8.2.3 Assessment of Adverse Events by the Investigator

The Investigator will assess the severity (intensity) of each adverse event as mild, moderate, or severe, and will also categorize each adverse event as to its potential relationship to study drug using the categories of yes or no.

Assessment of severity:

Mild – An event that is easily tolerated and generally not interfering with normal daily activities.

Moderate – An event that is sufficiently discomforting to interfere with normal daily activities.

Severe – An event that is incapacitating with inability to work or perform normal daily activities.

Causality assessment:

The relationship of an adverse event to the administration of the study drug is to be assessed according to the following definitions:

No (unrelated, not related, unlikely to be related) – The time course between the administration of study drug and the occurrence or worsening of the adverse event rules out a causal relationship and another cause (concomitant drugs, therapies, complications, etc.) is suspected.

Yes (possibly, probably, or definitely related) – The time course between the administration of study drug and the occurrence or worsening of the adverse event is consistent with a causal relationship and no other cause (concomitant drugs, therapies, complications, etc.) can be identified.

The definition implies a reasonable possibility of a causal relationship between the event and the study drug. This means that there are facts (evidence) or arguments to suggest a causal relationship.

The following factors should also be considered:

• The temporal sequence from study drug administration-

The event should occur after the study drug is given. The length of time from study drug exposure to event should be evaluated in the clinical context of the event.

• Underlying, concomitant, intercurrent diseases-

Each report should be evaluated in the context of the natural history and course of the disease being treated and any other disease the patient may have.

Concomitant drug-

The other drugs the patient is taking or the treatment the patient receives should be examined to determine whether any of them might be recognized to cause the event in question.

• Known response pattern for this class of study drug-

Clinical and/or preclinical data may indicate whether a particular response is likely to be a class effect.

Exposure to physical and/or mental stresses-

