The exposure to stress might induce adverse changes in the recipient and provide a logical and better explanation for the event.

• The pharmacology and PK of the study drug-

The known pharmacologic properties (absorption, distribution, metabolism, and excretion) of the study drug should be considered.

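### An adverse event with compatible timing and an identifiable other cause meets neither causality definition in Protocol 8.2.3, so sites may code it differently in the drug-related AE primary endpoint

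*Protocol*

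**What the plan says.** Protocol 8.2.3 has the investigator classify each adverse event's relationship to study drug "using the categories of yes or no", and gives a label and a definition for each category.

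- The first label is "No (unrelated, not related, unlikely to be related", and its definition is timing that "rules out a causal relationship and another cause (concomitant drugs, therapies, complications, etc.) is suspected".
- The second label is "Yes (possibly, probably, or definitely related", and its definition is timing "consistent with a causal relationship and no other cause (concomitant drugs, therapies, complications, etc.) can be identified".

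The section then says that the definition implies a reasonable possibility of causation, and explains: "This means that there are facts (evidence) or arguments to suggest a causal relationship". A list of further factors follows. Raters are to ask whether the event came after dosing, whether other drugs "might be recognized to cause the event in question", and whether stress might "provide a logical and better explanation for the event".

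Protocol 8.2.1 sets the standard for an adverse drug reaction. A causal link must be at least a reasonable possibility, which 8.2.1 glosses as a relationship that has not been excluded.

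The flag feeds the first primary endpoint (Protocol 7.1, SAP 2.3.1). SAP 3.6.1 tabulates patients with drug-related AEs by repeating the three words of the *Yes* label, and adds no coding rule of its own.

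**The concern.** A yes/no scale needs two categories that together cover every event. Here each definition joins a timing condition to a cause condition, and the two definitions differ on both conditions, so they are not complements. The case that matters is an event with plausible timing after dosing for which another cause can also be identified. Read literally, it is not *Yes*. It is not *No* either, because timing does not exclude the drug. The label and 8.2.1 point to related.

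About 7 sites (SAP 2.2.1) could settle this in different ways. A site that follows the literal *Yes* definition would leave the event out of the primary endpoint, while one that follows the label or 8.2.1 would count it. The tables would then mix two standards, and no reader could separate them.

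**Working it through.** **Step 1. Apply the two definitions to every combination.** The *No* definition speaks of a suspected cause and the *Yes* definition of an identified one, so the cause axis gets three levels.

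| Timing | No other cause suspected | Other cause suspected, not identified | Other cause identified |
|---|---|---|---|
| Compatible with the drug | Yes | Yes | **neither** |
| Rules the drug out | **neither** | No | No |

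Four of six cells are covered. If suspected and identified are merged, two of four are covered. The same two gaps appear both ways, so they do not depend on how the cause axis is cut.

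**Step 2. See whether other text settles the two open cells.**

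- *Timing rules the drug out, no other cause.* Under 8.2.1 this is not a reaction, because the relationship has been excluded. For an AE recorded before the first dose, the temporal factor in 8.2.3 gives the same answer. Nothing points the other way, so the event is *No*. This gap is one of literal wording only.
- *Timing compatible, other cause identified.* The *Yes* definition fails. The label word *possibly* suggests *Yes*. Under 8.2.1 the event is related unless the other cause explains it so fully that the drug is excluded. The factors on concomitant drugs and stress tell the rater to look for alternatives, but not how to code an event that has one. This cell stays open.

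One contested cell remains.

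**Step 3. Check the *unlikely* label.** An event judged unlikely has not been ruled out. The label makes it *No*. The *No* definition is not met, and 8.2.1 treats it as a reaction. If its timing is compatible and no other cause is identified, it even meets the literal *Yes* definition.

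**Step 4. Ask whether the contested cell will occur.** All patients take a statin, and Protocol 1.1 lists muscular intolerance and transaminitis among the limits of statin therapy. Protocol 5.2 reports a potential liver signal in one Phase 1 subject at 150 mg that was confounded with alcohol, and 5.7.1 allows limited alcohol on non-dosing days. Such events are foreseeable, but the documents do not support a count.

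**Step 5. Scale.** There are 4 × 12 = 48 patients. A patient whose only candidate event is recoded moves the arm by 1/12 = 8.3 points and the whole study by 1/48 = 2.1 points. As an assumption only, 0 to 3 such patients in an arm with no other drug-related AE would give 0/12 = 0%, 1/12 = 8.3%, 2/12 = 16.7% or 3/12 = 25.0%.

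**Step 6. Trace where the flag is used.** It drives the drug-related AE tables and the reporting of SAEs that arise after the reporting window (Protocol 8.4). The SAP's definition of a treatment-emergent AE also refers to a worsening relationship to study drug, so the flag can affect events that began before dosing. It is not used in the all-AE summaries, the CTCAE-graded laboratory tables (SAP 3.6.1, 3.6.2), the stopping guidelines (Protocol 9.2.3) or the individual discontinuation criteria (Protocol 8.1). SAEs through follow-up are reported whatever the flag says.

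**The case against.** The strongest reply is that a governing standard is already stated. The sentence after the definitions speaks of a reasonable possibility, 8.2.1 uses the same idea, and the factor list tells raters how to weigh the evidence. An experienced investigator would treat the definitions as loose wording around that judgement. Much of this stands. A reader might infer that half of all timing-by-cause combinations are unclassified and that the endpoint has no coding rule at all. The documents do not support that: one of the two open cells is settled as *No*, and a common interpretive standard exists. An alternative that is only suspected also still fits *Yes*, so the clash with *possibly* is confined to identified alternatives.

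The reply does not close the contested cell. The protocol directs raters to the definitions. The reasonable-possibility sentence is offered as what they imply, not as a replacement, and the factors are additional considerations. No text says which prevails when an alternative cause is present.

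Two further objections deserve an answer. First, any revised rule is still a judgement, so some variation between sites will remain. That is true, but an express instruction removes the part created by the wording. Second, eCRF guidance alone might be enough. It would be lighter, but it would leave a protocol definition in force that says something else.

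**Conclusion.** The point holds for one kind of event, compatible timing with an identifiable other cause, and for the mismatch between the *unlikely* label, the *No* definition and 8.2.1. It deserves correction because it affects how a primary endpoint is coded, and one clear rule resolves it. It does not threaten the study's conclusions: the safety analysis is descriptive (Protocol 9.2.1) and the main safety displays do not rely on the flag.

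Two stronger inferences should be resisted.

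- The 8.3 points is the resolution of any incidence in a 12-patient arm. It is not an estimate of error, since the number of affected patients is unknown.
- A tilt toward one arm is not expected. Investigators and clinical staff are blinded and post-randomization lipid levels are withheld from sites (Protocol 5.3).

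The conclusion rests on reading the definitions as written, and on the assumption that an identified alternative does not by itself exclude a contribution from the drug.

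**What to change.** In Protocol 8.2.3, replace the two definitions with one exhaustive rule.

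- *Yes*: there is a reasonable possibility, supported by facts or arguments, that study drug caused or contributed to the event, whether or not another cause is identified.
- *No*: all other events.

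State that the listed factors are used to apply this rule.

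Leave 8.2.1 unchanged. It underlies the definition of an unexpected reaction (8.2.2) and SUSAR reporting (8.6). Changing it so that unlikely but not excluded events fall outside would narrow that reporting. Reconcile the *unlikely* label in 8.2.3 with 8.2.1 instead, either by removing it from *No* or by stating how such an event is coded, so that both sections give the same answer.

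Have SAP 3.6.1 cite the 8.2.3 rule rather than repeat the label. If AEs have already been coded, the blinded site investigators should re-review them under the rule before database lock. The sponsor should not do this, because it is open to treatment (Protocol 3.1).

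Separately, base the by-arm AE summaries in SAP 3.6.1 on the treatment-emergent AEs already defined there, and list pre-dose events. AEs are collected from screening (Protocol 8.2), yet the overview counts any AE.

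The cost is a protocol amendment with full review and approval (Protocol 12.1), matching eCRF guidance, two SAP wording edits and, if coding has begun, one re-review in a study of about 48 patients. No new table is needed. The downside is that somewhat more events will be coded as related, including on placebo.

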8.2.4 Adverse Events of Special Interest

The Investigator will monitor each patient for clinical and laboratory evidence for adverse events of special interest (AESIs) throughout the patient's participation in this study as defined below.

The Investigator will assess and record any additional information on the AESI in detail on an adverse event form which must be submitted within 24 hours of awareness of the event.

For this study, AESIs include the following:

- CTCAE (current version) Grade 2 or higher ALT measurements confirmed on repeat measurement
- Severe or serious injection site reactions (ISRs), ISRs that are associated with a recall phenomenon (reaction at the site of a prior injection with subsequent injections), recurrent ISRs that are increasing in severity, or ISRs that lead to temporary dose interruption or permanent discontinuation of study drug.
- An ISR is defined as a local reaction at or near the site of injection. "At or near" the injection site includes reactions at the injection site, adjacent to the injection site, or a reaction which may shift slightly away from the injection site due to gravity (e.g., as may occur with swelling or hematoma). A systemic reaction which includes the injection site (e.g., generalized urticaria, other distinct entities or conditions like lymphadenopathy that may be near the injection site) is not considered an ISR

Adverse events of special interest must be recorded in the eCRF.

8.3 Serious Adverse Events

An adverse event or adverse reaction is considered serious if, in the view of either the Investigator or Sponsor, it results in any of the following outcomes:

- Death.
- A life-threatening adverse event.

Note: An adverse event or adverse reaction is considered "life-threatening" if, in view of either the Investigator or Sponsor, its occurrence places the patient at immediate risk of death. It does not include an event that, had it occurred in a more severe form, might have caused death.

• Hospitalization or prolongation of existing hospitalizations.

Note: Any hospital admission with at least 1 overnight stay will be considered an inpatient hospitalization. An emergency room or urgent care visit without hospital admission will not be recorded as a SAE under this criterion, nor will hospitalization for a procedure scheduled or planned before signing of informed consent, or elective treatment of a preexisting condition that did not worsen from Baseline. However, unexpected complications and/or prolongation of hospitalization that occur during elective surgery should be recorded as adverse events and assessed for seriousness. Admission to the hospital for social or situational reasons (i.e., no place to stay, live too far away to come for hospital visits, respite care) will not be considered inpatient hospitalizations.

- A persistent or significant disability/incapacity or substantial disruption of the ability to conduct normal life functions.
- A congenital anomaly/birth defect.
- An important medical event.

Note: Important medical events that do not meet any of the above criteria may be considered an SAE when, based upon appropriate medical judgment, they may jeopardize the patient and may require medical or surgical intervention to prevent one of the outcomes listed above. Examples of such medical events include allergic bronchospasm requiring intensive treatment in an emergency room or at home, blood dyscrasias or convulsions that do not result in inpatient hospitalizations, or the development of drug dependency.

8.4 Serious Adverse Event Reporting - Procedures for Investigators

Initial reports

All SAEs occurring from the time of informed consent until completion of the follow-up period must be reported to Medpace Clinical Safety within 24 hours of the knowledge of the occurrence. After the 30-day reporting window, any SAE that the Investigator considers related to study drug must be reported to Medpace Clinical Safety or the Sponsor/designee.

To report the SAE, complete the SAE form electronically in the electronic data capture (EDC) system for the study. When the form is completed, Medpace Safety personnel will be notified electronically by the EDC system and will retrieve the form. If the event meets serious criteria and it is not possible to access the EDC system, send an email to Medpace Safety at medpace-

[contact] or call the Medpace SAE reporting line (phone number listed below), and fax/email the completed paper SAE form to Medpace (contact information listed in Section 8.7) within 24 hours of awareness. When the EDC system becomes available, the SAE information must be entered within 24 hours of the system becoming available.

Follow-up reports

The Investigator must continue to follow the patient until the SAE has subsided or until the condition becomes chronic in nature, stabilizes (in the case of persistent impairment), or the patient dies.

Within 24 hours of receipt of follow-up information, the Investigator must update the SAE form electronically in the EDC system for the study and submit any supporting documentation (e.g., patient discharge summary or autopsy reports) to Medpace Clinical Safety via fax or email. If it is not possible to access the EDC system, refer to the procedures outlined above for initial reporting of SAEs.

8.5 Pregnancy Reporting

If a patient becomes pregnant during the study or within the safety follow-up period, the Investigator is to stop dosing with study drug(s) immediately and the patient should be withdrawn from the study. Early termination procedures should be implemented at that time.

A pregnancy is not considered to be an adverse event or SAE; however, it must be reported to Medpace Clinical Safety within 24 hours of knowledge of the event. Medpace Clinical Safety will then provide the Investigator/site the Exposure In Utero (EIU) form for completion. The Investigator/site must complete the EIU form and fax/email it back to Medpace Clinical Safety.

If the female partner of a male patient becomes pregnant while the patient is receiving study drug or within the safety follow-up period, the Investigator should notify Medpace Clinical Safety as described above.

The pregnancy should be followed until the outcome of the pregnancy, whenever possible. Once the outcome of the pregnancy is known, the EIU form should be completed and faxed/emailed to Medpace Clinical Safety. If the outcome of the pregnancy meets the criteria for immediate classification as an SAE (i.e., postpartum complication, spontaneous abortion, stillbirth, neonatal death, or congenital anomaly), the Investigator should follow the procedures for reporting an SAE.

8.6 Expedited Reporting

The Sponsor/designee will report all relevant information about Suspected Unexpected Serious Adverse Reactions (SUSAR) that are fatal or life-threatening as soon as possible to the Food and Drug Administration (FDA), Health Canada, and to the Central Ethics Committee, and in any case no later than 7 days after knowledge by the Sponsor/designee of such a case. Relevant follow-up information will subsequently be communicated within an additional 8 days.

All other SUSARs will be reported to the FDA, Health Canada, and to the Central Ethics Committee, as soon as possible but within a maximum of 15 days of first knowledge by the Sponsor/designee.

The Sponsor/designee will also report any additional expedited safety reports required in accordance with the timelines outlined in country-specific legislation.

The Sponsor/designee will also inform all Investigators as required per local regulation.

The requirements above refer to the requirements relating to IMP.

8.7 Special Situation Reports

Special situation reports include reports of overdose, misuse, abuse, medication error, and reports of adverse reactions associated with product complaints.

- Overdose: Refers to the administration of a quantity of a medicinal product given per administration or cumulatively (accidentally or intentionally), which is above the maximum recommended dose according to the protocol. Clinical judgement should always be applied. In cases of a discrepancy in the drug accountability, overdose will be established only when it is clear that the patient has taken additional dose(s) or the Investigator has reason to suspect that the patient has taken additional dose(s).
- **Misuse:** Refers to situations where the medicinal product is intentionally and inappropriately used not in a way that is not in accordance with the protocol instructions or local prescribing information and may be accompanied by harmful physical and/or psychological effects.
- **Abuse:** Is defined as persistent or sporadic, intentional excessive use of a medicinal product, which is accompanied by harmful physical or psychological effects.
- **Medication error:** Is any unintentional error in the prescribing, dispensing, or administration of a medicinal product by a healthcare professional, patient, or consumer, respectively. The administration or consumption of the unassigned treatment and administration of an expired product are always reportable as medication errors; cases of patients missing doses of investigational product are not considered reportable as medication error.
- **Product complaint:** Is defined as any written, electronic, or oral communication that alleges deficiencies related to the identity, quality, durability, reliability, safety, effectiveness, or performance of a drug or device after it is released for distribution. A Special Situations Report form will only be completed if a complaint is associated with an adverse drug reaction.

All special situation events as described above must be reported on the Special Situations Report form and faxed/emailed to Medpace Clinical Safety (contact information listed below) within 24 hours of knowledge of the event. All adverse events associated with these Special Situations Report forms should be reported as adverse events or SAEs as well as recorded on the adverse event eCRF and/or the SAE report form. Details of the symptoms and signs, clinical management, and outcome should be provided, when available.

8.8 Injection Site Assessment

The SC injection site may be marked and mapped for later observation. Visual assessment of the injection site will be conducted by an Investigator (or designee) at the times indicated in the

Schedule of Procedures in Appendix A. Categorical scales will be used to score injection site reaction severity, pain, induration, erythema and edema. If a local reaction around the injection site occurs, photographs may be obtained.

8.9 Clinical Laboratory Evaluations

Blood and urine samples will be collected for clinical laboratory evaluations (including clinical safety chemistry; hematology; coagulation parameters including fibrinogen; cytokine; complement activation; urinalysis; and serology) at the times indicated in the Schedule of Procedures in Appendix A. Clinical laboratory analytes are listed in Appendix B.

An Investigator (or designee) will perform a clinical assessment of all clinical laboratory data.

8.10 Vital Signs

Sitting BP, heart rate, respiration rate, and oral body temperature will be assessed at the times indicated in the Schedule of Procedures in Appendix A. Vital signs may also be performed at other times if judged to be clinically appropriate or if the ongoing review of the data suggests a more detailed assessment of vital signs is required.

All measurements will be performed singly and repeated once if outside the relevant clinical reference range.

Patients must be sitting for at least 5 minutes before vital signs measurements.

8.11 12-Lead Electrocardiograms

Resting 12-lead ECGs will be performed in triplicate and recorded using the automatic data generated by the ECG as the source data. Recordings are to occur after the patient has been supine and at rest for at least 5 minutes at the times indicated in the Schedule of Procedures in Appendix A.

Additional 12-lead ECGs may be performed at other times if judged to be clinically appropriate or if the ongoing review of the data suggests a more detailed assessment of ECGs is required. The Investigator (or designee) will perform a clinical assessment of each 12-lead ECG.

